### 7.3.11 Subgroup and Exploratory Analysis

Subgroup analyses will be performed to explore the influence of the baseline variables, and the individual TC therapy administered, on the efficacy outcomes of CR rate and OS, and to evaluate the treatment effect at different levels of each baseline variable:

- Age (<75, ≥75).
- AML category (primary, secondary).
- Baseline cytogenetic risk (poor-risk, others [No/Unknown]).
- Baseline ECOG PS (0-1, 2-3).
- Baseline BM blasts (≤30%, >30%).
- Baseline total WBC counts (<20,000/μL, ≥20,000/μL).
- Study center region (North America, Europe, Asia-Pacific, ROW).
- Race (White, Black, Asian, Other).
- Presence of baseline genetic abnormalities such as FLT3, NPM1, and CEBPA (for each gene: yes, no).
- Individual TC (cytarabine, decitabine, azacitidine) compared with guadecitabine treatment for subjects randomized under that preselected TC option.

For subgroup analysis of CR, the OR of guadecitabine versus TC and associated 95% CIs will be provided for subgroups defined by categories of each variable listed above (except Individual TC). The intention is to descriptively display the treatment effect for each of these subgroups on Forest plots.

For subgroup analysis of OS, the HR of guadecitabine versus TC and associated 95% CIs will be provided for subgroups defined by categories of each variable listed above (except individual TC). Again, the intention is to descriptively display the treatment effect for each of these subgroups on Forest plots.

In addition, the CR and OS will be compared between subjects who were randomized to guadecitabine versus those who were randomized to TC within the subjects who were preassigned to a particular TC treatment. This comparison will be done for each of the three preassigned TC patient groups separately.

### 7.3.12 Dealing with Technical Issues Caused by Small Cell Count

If technical issues (such as non-convergence or unstable variance) arise due to small cell counts caused by too many levels of stratification variables, the stratification variables will be collapsed in the following order, until the technical issues have been resolved:

- 1) Collapse North America and EU into one level of geographic region, resulting in a new two-level geographic region variable (North America/EU vs. ROW).
- 2) Collapse geographic regions completely (combine North America, EU and ROW).
- 3) Collapse geographic regions completely and collapse Age categories ( $\geq 75$  and  $< 75$  years).

### 7.3.13 Dealing with Non-Proportional Hazards in OS and PFS Analyses

In supportive analyses, the proportional hazards assumption for treatment over time will be assessed by including (effect of) treatment as a time-dependent covariate in the Cox regression model. The Cox regression analysis will be conducted with the time-dependent covariate (Treatment\*Log(time)) in the model, where the variable Treatment has two levels, guadecitabine or TC, and Log(time) is natural log of survival time. A below 0.05  $p$  value of this test is an indicator that the proportional hazards assumption may not hold.

If the proportional hazards assumption does not hold, the following additional analyses will be conducted to assess the treatment effect over different time intervals or at different time points.

- 1) A piece-wise Cox model will be conducted for evaluating a separate HR for each piece or interval. The cut-off times for the piece-wise Cox model are  $>0$  to 6 months,  $>6$  to 12 months,  $>12$  to 18 months,  $>18$  to 24 months and  $>24$  months. For ease of calculation, one month is defined as 30 days for analyses conducted in this study.

- 2) The survival rates between the two treatment arms at each of the 6-month, 12-month, 18-month, and 24-month time points will be evaluated for the treatment effect at these time points. The stratified Kaplan-Meier estimates of survival probabilities and the corresponding standard errors based on the Greenwood formula ([Kalbfleisch and Prentice 1980](#)) will be used for constructing this analysis.

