7.4 Emergency Treatment for Subjects with Highly Proliferative Progressive AML

This study allows enrollment of subjects with proliferative AML (total WBC count \geq 20,000). For those subjects, pretreatment with hydroxyurea or leukapheresis before randomization may be warranted to decrease total WBC count. However, hydroxyurea, leukapheresis, or other anti-leukemia therapy is not allowed after subjects are randomly assigned to study treatment. After the first cycle of study treatment, subjects who continue to have rapidly increasing total WBC counts with increasing PB blasts % are allowed to start the next study treatment cycle earlier than Day 29. Early administration of study treatment allows such subjects to remain on study and potentially benefit from treatment. Benefit may require multiple cycles given the lower intensity treatments in this study (as compared with intensive remission induction therapy).

Any deviation from the study schedule should be clearly explained and documented in the eCRF. After the proliferative phase subsides and the subject responds to treatment, the standard treatment cycle duration of 28 days should be resumed and maintained.

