### 7.3.3 Overall Survival

For the OS analysis, survival time is defined as the number of days from the day the subject was randomly assigned to study treatment to the date of death (regardless of cause).

$$\text{Survival time in days} = (\text{earliest date of death or censoring} - \text{date of randomization})$$

Survival time will be censored on the last date the subject is known alive with no event of death. OS curves will be estimated using Kaplan-Meier method and formally compared between the two treatment groups using a 2-sided stratified log-rank test, stratified by the same stratification factors used at randomization. The null and alternative hypotheses are:

- **Null hypothesis  $H_0$ :** Survival curves are the same between the two treatment arms
- **Alternative hypothesis  $H_1$ :** Survival curves are different between the two treatment arms

If the CR rate analysis is significant, OS will be tested at an alpha level of 0.05; without a significant CR rate test result, OS will be tested at an alpha level of 0.01, as described in Section 7.3.7. The stratification variables will include age (<75 or  $\geq$ 75 years), ECOG performance status (0-1, 2-3), study center region (North America, Europe, ROW), and secondary AML or poor-risk cytogenetics (Yes, No/Unknown). The median (and quartiles) duration of OS and the associated 95% CI for each treatment arm will be estimated using the Kaplan-Meier method and the  $\log(-\log(\cdot))$  transformation for the survival function. The 12-month survival rate estimate will also be provided for each treatment arm.

In addition, the HR and its 95% CI will be estimated using a Cox proportional-hazard model with treatment group as the independent variable and stratified by the same randomization stratification factors as used for the log-rank test. In a supportive analysis, the assumption of proportional hazards will be evaluated to assist interpretation of the Cox regression analysis results.

The following sensitivity analyses will be conducted for the co-primary endpoint of OS for evaluating robustness of the treatment effect:

- 1) The OS will be analyzed using Kaplan-Meier method and compared between the guadecitabine and TC using log-rank test without stratification.

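### SAP 7.3.13 leaves it to a low-power proportional-hazards test whether interval hazard ratios and landmark survival contrasts are reported; they should be reported regardless

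*SAP*

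**What the plan says.** SAP 7.3.3 and 7.3.6 summarise OS and PFS by a stratified log-rank test, Kaplan-Meier medians and quartiles, and one stratified Cox hazard ratio. In a supportive analysis, "the assumption of proportional hazards will be evaluated to assist interpretation of the Cox regression analysis results".

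SAP 7.3.13 sets out that check. A treatment by log(time) term is added to the Cox model, where "Log(time) is natural log of survival time", and a p value below 0.05 "of this test is an indicator that the proportional hazards assumption may not hold". It then states: "If the proportional hazards assumption does not hold, the following additional analyses will be conducted to assess the treatment effect over different time intervals". Two analyses follow:

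- "A piece-wise Cox model will be conducted for evaluating a separate HR for each piece or interval", with cuts at 6, 12, 18 and 24 months.
- A comparison of the arms' stratified Kaplan-Meier survival probabilities at 6, 12, 18 and 24 months, with Greenwood standard errors.

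No other criterion for a failed assumption is given, and no size of departure is named as tolerable.

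Several time-related outputs do not depend on the check. For OS these are the Kaplan-Meier curves, medians and quartiles with 95% CIs, and the 12-month rate per arm (SAP 7.3.3). The 30- and 60-day all-cause mortality percentages (SAP 7.4.3) are also unconditional, and Protocol 11.7 compares them by Chi-square.

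**The concern.** When the pre-test is not significant, the plan gives no interval hazard ratio and no between-arm survival contrast with a standard error at any landmark. The between-arm size of the OS effect then rests on one averaged hazard ratio. A test with little power against a moderate change in effect will often withhold these contrasts when they would be informative, and the set of OS analyses reported depends on the OS data.

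This matters here because Protocol 4.2 gives OS the task of confirming that severe toxicity causes no loss of survival. An averaged hazard ratio answers that question poorly if early and later effects differ. At stake is the interpretation of OS and PFS, not the validity of the primary test.

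**Working it through.** **Inputs.** From SAP 4.0: 800 subjects, 1:1; medians 7 and 9 months; 670 deaths; 90% power; two-sided alpha 0.05; uniform accrual over 21 months plus 12 months of follow-up. From SAP 7.3.13: treatment by ln(time), threshold 0.05. The design assumes a constant hazard ratio, so every non-proportional pattern below is an assumption.

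**The plan's own figure.** HR = 7/9 = 0.778 and ln HR = -0.2513. Schoenfeld events = 4 × (1.960 + 1.282)² / 0.2513² = 666. Power at 670 deaths is 0.902. Exponential survival with the stated accrual and follow-up gives 670.0 expected deaths. The stated design reproduces.

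**Power of the proportional-hazards test.** Simulated trials had 400 per arm, TC exponential with median 7 months, piecewise-constant hazard ratios, a cut at the 670th death and no dropout. Each had an unstratified Cox fit with treatment and treatment × ln(time), and a two-sided Wald test at 0.05. Under a constant hazard ratio the test rejected 4.8% (HR 1.0) and 5.0% (HR 0.78), so its size is right. Miss rates (p≥0.05), as ranges over repeat runs:

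| Assumed OS pattern | Missed |
|---|---|
| HR 1.0 to 3 months, then 0.70 | 59–62% |
| HR 1.0 to 6 months, then 0.65 | 45–48% |
| HR 1.25 to 2 months, then 0.78 | 44–46% |
| HR 1.3 to 2 months, then 0.70 | 20–22% |
| HR 1.5 to 2 months, then 0.70 | 5–6% |

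At 3,000 trials the Monte Carlo standard error is at most √(0.25/3000) = 0.9 point. Other patterns widen the range. No effect to 2 months then 0.75 is missed 78% of the time; no effect to 6 months then 0.50 is missed 9%.

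**The first piece, >0 to 6 months.** Take HR 1.3 to 2 months, then 0.70. The TC hazard is ln 2 / 7 = 0.0990 per month.

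- Deaths in months 0–2: 400 × 0.180 + 400 × 0.227 = 163. In this pattern 60-day mortality is 18.0% on TC and 22.7% on guadecitabine.
- Deaths in months 2–6: TC 400 × (0.820 - 0.552) = 107; guadecitabine 400 × 0.773 × (1 - e^(-4 × 0.0990 × 0.70)) = 75; total 182.
- Event-weighted log HR: (163 × 0.262 - 182 × 0.357) / 345 = -0.065, so HR is about 0.94.

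Even when the piece-wise model is triggered, its first interval would show a value just below 1 for this pattern.

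**Precision if always reported.** The 95% limits of an interval HR are about ×/÷ exp(1.96 × 2/√d), where d is the number of deaths in the interval.

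- Months 0–6 at the design rates: 179 + 148 = 327 deaths, factor 1.24.
- Months 0–2: 129 to 163 deaths across the patterns, factor 1.41 to 1.36.
- Months 18–24: about 39 deaths, factor 1.9.
- After 24 months: about 13 deaths, factor 3.0.
- Six-month survival of 55% and 63%: the difference has 95% limits of ±1.96 × √(0.55 × 0.45/400 + 0.63 × 0.37/400) = ±6.8 points.

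**The case against.** The strongest reply is that the gated analyses are supportive, their trigger is pre-specified, and the reader is not left without time-related information. The unconditional outputs would show a gross early excess of deaths, and Protocol 11.0 leaves room for additional sensitivity analyses. This stands. It rules out the reading that the plan shows a changing OS effect only when the test is significant. What is gated is the between-arm quantification by interval and landmark.

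Three other stronger readings are tempting, and the documents do not support them.

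- A reader might infer that a non-significant test is offered as proof of a constant effect. The SAP calls p<0.05 an indicator and does not say what p≥0.05 shows.
- A reader might infer that the protocol itself expects early harm or delayed benefit on guadecitabine. Protocol 7.4 does say "Benefit may require multiple cycles given the lower intensity treatments in this study", but this covers both arms and sets them against intensive induction. Protocol 2.1 describes early mortality as comparable with the TC agents, although febrile neutropenia was higher.
- A reader might quote a single miss-rate range as a property of the plan. The rate depends on the assumed pattern and runs from about 6% to 78% over the patterns tried.

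The reply also has force against a cut at 2 months. With HR 1.3 and 163 deaths, the >0 to 2 month interval has 95% limits of about 0.96 to 1.77 (1.3 ÷ and × 1.36) and would exclude 1 in about 38% of trials. A 60-day mortality comparison has the same power. The reply does not justify the gate: none of the unconditional outputs gives a between-arm contrast from randomization at 6, 12, 18 or 24 months. The early-mortality table covers treated subjects from C1D1 only.

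**Conclusion.** The point holds as a reporting weakness with a cheap remedy. A test that misses moderate changes in effect in roughly 20% to 60% of trials under the tabulated patterns, though only about 6% under the strongest early harm there, should not decide whether the interval and landmark contrasts appear. The size rests on assumed OS patterns, exponential TC survival with a 7-month median, no loss to follow-up and an unstratified test model (SAP 7.3.13 does not say whether that model is stratified). No PFS simulation was done; the wording applies to PFS, but these miss rates do not transfer. The type I error and power of the primary stratified log-rank test are unaffected.

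**What to change.** In SAP 7.3.13, delete the condition that proportional hazards must be found not to hold. State that, for OS and PFS, the stratified Kaplan-Meier survival differences with 95% CIs at 6, 12, 18 and 24 months and the piece-wise hazard ratios are always reported as descriptive, supportive analyses. Keep the treatment by log(time) p value as description only, and add that p≥0.05 is not evidence of a constant effect.

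Optionally, split the first piece into >0 to 2 and >2 to 6 months, so that early harm and later benefit are not averaged. This aids presentation more than detection.

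The cost is a wording change and tables already specified, plus one cut-point if the option is taken. No new data and no alpha are needed. The downside is several more descriptive contrasts without multiplicity control: five pieces (six with the split) and four landmarks for each of two endpoints. Intervals are wide for >0 to 2 months (about ×/÷1.4) and wider after 18 months, where few deaths occur; the tables should give the number of deaths in each piece.

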## 7.4 Safety Variables and Analyses

All safety analyses will be performed using the Safety Analysis Set which includes data from all subjects who receive any amount of study treatment (guadecitabine or TC; see [Section 5.3](#)).

Safety is assessed by subject-reported and investigator-observed AEs, and 30-day and 60 day all-cause mortality, along with concomitant medications, physical examination, clinical laboratory tests (hematology, serum chemistry, and urinalysis), vital signs, ECOG performance status, and ECGs. Safety is also assessed by exposure to guadecitabine or TC, reasons for discontinuation, deaths and causes of deaths.

All safety data collected during the study will be included in the study database. All safety data collected during the study will be used for generation of safety summary tables, with the exception of AEs and medications. The AE and medication summary tables will only include treatment-emergent AEs and concomitant medications as defined in [Sections 7.4.2 and 7.4.4](#).

### 7.4.1 Study Treatment Exposure

Cycle 1 Day 1 is defined as the first day of study treatment after randomization; cycle days are counted sequentially thereafter. Cycle 2 Day 1 is the first day of Cycle 2 regardless of treatment delays. The designated cycle duration is 28 days but any cycle could be prolonged to >28 days to allow blood count recovery if deemed clinically necessary. This convention for determining the start and stop dates for cycles is maintained until treatment is permanently discontinued. For easy presentation, Cycle x Day y is often abbreviated as CxDy in this document and statistical outputs.

Frequency counts and percentages of dose cycles received, dose cycles delayed, and dose reduced cycles will be summarized by treatment group. Summary statistics of number of cycles received, as well as percentages of intended dose received, will also be provided by treatment group. Dose delayed cycles are identified by the study site and entered into the electronic data capture (EDC) system. A dose reduced cycle is defined as a cycle in which the dose was reduced by 20% or more, compared with the planned Cycle 1 dose. Percentage of intended dose is equal to actual total dose divided by planned total dose through the last treatment cycle. Both completed or partially completed dose cycles are counted in these summaries.

## 7.4.2 Adverse Events

AE terms reported by study subjects or observed by investigators will be mapped to the appropriate System Organ Class (SOC) and Preferred Term (PT) according to the Medical Dictionary for Regulatory Activities (MedDRA). Severity of AE will be graded using Common Terminology Criteria for Adverse Events (CTCAE) version 4.03.

Treatment-emergent AEs are defined as events that first occurred or worsened after the first dose of study drug given on C1D1 until 30 days after the last dose of study treatment or the start of an alternative anti-leukemia treatment, whichever occurs first, with the following exceptions: events that occurred after 30 days beyond the last dose of study treatment or the start of an alternative anti-leukemia treatment will also be considered treatment-emergent if the events are both serious and related to the study treatment. For the purpose of determining whether an AE is a treatment-emergent AE, incomplete AE start and stop dates will be imputed conservatively following the data programming standards as detailed in the Astex Data Programming Conventions.

All AE data collected in the study database will be listed, including those that are not treatment emergent. However, safety tables will be generated based only on Treatment-emergent AEs.

An overall safety summary table containing counts and percentages of subjects with any AE, any AE Grade  $\geq 3$ , AE leading to treatment discontinuation, any serious AE (SAE), SAE leading to death, and other subjects with an SAE will be produced by treatment group. A similar table with related AE counts will also be produced by treatment group. Related events are those that the investigator considered to be suspected to be related to study treatment as described in the study protocol.

The number and percentage of subjects experiencing AEs will be summarized by MedDRA SOCs (sorted alphabetically) with PTs sorted alphabetically within each SOC, and by CTCAE grade. The number and percentage of subjects experiencing AEs will also be summarized by PT and sorted by event frequency. Related AEs, serious AEs, and related serious AEs will be summarized similarly. In summarizing AEs, if a subject reports the occurrence of a particular AE more than once, the event is only counted once with its worst CTCAE grade.

Treatment-site events (including events at the injection site) are of special interest. These events will be tabulated separately. Since it is expected that SC administration will be associated with more injection site events, a separate table will be produced to compare guadecitabine SC injection events to low dose Ara C (LDAC) SC injection events in subjects randomized under the preselected LDAC TC; and a similar table comparing guadecitabine SC to azacitidine (only those subjects receiving azacitidine by SC route) under the preselected azacitidine TC option.

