8. Total serum bilirubin $> 2.5 \times$ ULN, except for subjects with Gilbert's Syndrome for whom direct bilirubin is $< 2.5 \times$ ULN, or liver cirrhosis or chronic liver disease Childs-Pugh B or C.
9. Known active human immunodeficiency virus (HIV), hepatitis B virus (HBV), or hepatitis C virus (HCV) infection. Inactive hepatitis carrier status or low viral hepatitis titer on antivirals is allowed.
10. Known significant mental illness or other condition such as active alcohol or other substance abuse or addiction that, in the opinion of the investigator, predisposes the subject to high risk of noncompliance with the protocol.
11. Refractory congestive heart failure unresponsive to medical treatment; active infection resistant to all antibiotics; or advanced pulmonary disease requiring > 2 liters per minute (LPM) oxygen.

Study Treatment:

- SGI-110: 60 mg/m² SGI-110 given SC daily on Days 1-5 in 28-day cycles. Treatment should be given for at least 6 cycles in the absence of unacceptable toxicity or disease progression requiring alternative therapy. Beyond 6 cycles, treatment should continue as long as the subject continues to benefit based on investigator judgment.
- TC: before randomization, subjects will be assigned by the investigator to 1 of the following treatment regimens (dose, schedule, and administration route; other treatment parameters, such as duration of treatment and dose adjustment guidelines, should follow locally approved prescribing information and institutional standard practice):
 - 20 mg cytarabine given SC BID on Days 1-10 every 28 days.
 - 20 mg/m² decitabine given IV daily on Days 1-5 every 28 days.
 - 75 mg/m² azacitidine given IV or SC daily on Days 1-7 every 28 days.

Study Endpoints:

Co-primary Endpoints

- CR rate based on modified International Working Group (IWG) 2003 AML Response Criteria.
- OS, defined as the number of days from randomization to death.

Secondary Endpoints

- CRc (CR+CRi+CRp) rate.
- Number of days alive and out of the hospital.
- PFS, defined as the number of days from randomization to disease progression or death, whichever occurs first.
- Number of red blood cell (RBC) or platelet transfusions (units) over the duration of the study treatment.
- Health-related QOL by EQ-5D (consisting of the EQ-5D-5L descriptive system and the EQ Visual Analogue Scale [EQ VAS]).
- Duration of CR, defined as the time from first CR to time of relapse.
- Incidence and severity of adverse events (AEs).

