7.1.2 SGI-110 Regimens and Administration

The SGI-110 regimen for this study is 60 mg/m² given Daily×5 (Days 1-5 in a 28-day cycle) for at least 6 cycles in the absence of unacceptable toxicity or AML progression for which the investigator intends to offer an alternative therapy. Beyond 6 cycles, treatment should continue as long as the subject continues to benefit based on investigator judgment. In the ongoing phase 2 dose expansion study (Section 1.3.2.2), some subjects responded late to treatment: of 51 treatment-naïve elderly AML subjects, 2 subjects responded, and another 2 subjects improved their response status from CRi or CRp to CR, after more than 6 treatment cycles with SGI-110.

Administer SGI-110 by SC injection, preferably in the abdominal area, upper thigh, or arm. The total amount (in mg) of SGI-110 to be administered is determined by body surface area (BSA). In calculating BSA, use actual heights and weights. Do not adjust to "ideal" body weight. The institutional standard for calculating BSA is acceptable.

Take care to avoid intradermal injection, as this may result in injection site pain (see Section 8.0).

Additional guidelines regarding SC injection will be detailed in the study procedures manual.

Investigators are prohibited from supplying SGI-110 to any subject not enrolled in this study or to any physicians or scientists except those designated as sub-investigators. The investigator must ensure that subjects receive SGI-110 only from personnel who fully understand the procedures for administering the study treatment.

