7.2 Treatment Choice (TC) Active Comparator

TC will be one of the following treatment regimens (dose, schedule, and administration route) based on regimens approved by regulatory agencies, on published randomized studies, and on recommendations by the NCCN, European Leukemia Net, and European Society for Medical Oncology:

- 20 mg cytarabine given SC twice daily (BID) on Days 1-10 every 28 days.
- 20 mg/m² decitabine given IV daily on Days 1-5 every 28 days.
- 75 mg/m² azacitidine given IV or SC daily on Days 1-7 every 28 days.

Other use and treatment parameters of TC drugs (such as duration of treatment and dose adjustment guidelines) should follow locally approved prescribing information and institutional standard practice.

Examples of locally approved prescribing information are the following: [Cytarabine 2008](#), [Dacogen 2010](#), [Vidaza 2014 \(USA\)](#); and [Cytarabine 20mg/ml 2014](#), [Dacogen 50 mg powder for concentrate for solution for infusion 2014](#), [Vidaza 25 mg/ml powder for suspension for injection 2014 \(UK\)](#).

If a subject must discontinue TC study treatment, alternative therapy should be determined by the physician or institutional standard practice. Subjects randomly assigned to TC study treatment will not be allowed to receive SGI-110 as alternative therapy.

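### Adverse events are summarised only as crude percentages over a window whose length follows time on treatment, so unequal exposure could overstate or mask a toxicity difference

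*SAP*

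**What the plan says.** SAP 7.4.2 defines treatment-emergent AEs as those that start or worsen "after the first dose of study drug given on C1D1 until 30 days after the last dose of study treatment", with an earlier stop if another anti-leukaemia therapy begins. Later events "will also be considered treatment-emergent if the events are both serious and related to the study treatment".

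The summaries are counts and percentages of subjects: "The number and percentage of subjects experiencing AEs will be summarized by MedDRA SOCs", then by preferred term and grade, with related and serious AEs handled the same way. Repeats do not add: "if a subject reports the occurrence of a particular AE more than once, the event is only counted once with its worst CTCAE grade". Protocol 11.7 also plans incidence tables only.

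The rules for treatment length differ by arm. For SGI-110, the Protocol synopsis says "Treatment should be given for at least 6 cycles in the absence of unacceptable toxicity or disease progression requiring alternative therapy", and Protocol 7.1.2 adds "Beyond 6 cycles, treatment should continue as long as the subject continues to benefit based on investigator judgment". For TC, Protocol 7.2 says "Other use and treatment parameters of TC drugs (such as duration of treatment and dose adjustment guidelines) should follow locally approved prescribing information" and institutional practice.

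Exposure (cycles received, delayed and reduced, and percentage of intended dose) is tabulated in SAP 7.4.1 but is not a denominator for any AE summary. The only fixed-window safety measure is 30- and 60-day all-cause mortality (SAP 7.4.3). Per-patient-year rates are planned for days alive and out of hospital (SAP 7.3.5) and for transfusions (Protocol 11.6.8), but not for AEs.

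**The concern.** A percentage of subjects with at least one event rises with the time over which events are counted. Here that time is set by how long each subject stays on treatment. The two arms work under different duration rules, the trial is open-label, and the sample-size section assumes median survival of 9 months on SGI-110 against 7 on TC. Realised time at risk could therefore differ by arm, and no planned AE summary takes account of it.

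Incidence and severity of AEs is a named secondary endpoint (SAP 3.2.2). Protocol Table 10 already shows more Grade 3 or higher febrile neutropenia on SGI-110 in Phase 2 (51%) than in the published comparator trials (25% to 32% where reported), so the Phase 3 tables will be read with that question in mind. If SGI-110 is given for longer, crude percentages could make it look worse than its risk per month. If it is given for a shorter time, they could hide real toxicity. The same applies to the tables that SAP 7.0 plans against each TC option.

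**Working it through.** **Inputs.** The documents give no figure for the AE comparison, no treatment durations and no AE hazards, so there is no stated AE result to reproduce. The only plan figures used are the survival medians, 9 and 7 months. They fit the plan's event count: Schoenfeld's formula at a hazard ratio of 7/9, 90% power and two-sided 0.05 gives 666 deaths against the stated 670. All other inputs below are assumptions, shown over a range. The AE hazard *h* is set equal in both arms throughout, so any gap is spurious.

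**Step 1. Constant hazard, exponential time at risk with mean *m* months.** Crude incidence = h / (h + 1/m).

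| h per month | m = 6 | m = 4 | gap (points) | m = 5 | m = 3 | gap (points) |
|---|---|---|---|---|---|---|
| 0.05 | 23.1% | 16.7% | 6.4 | 20.0% | 13.0% | 7.0 |
| 0.10 | 37.5% | 28.6% | 8.9 | 33.3% | 23.1% | 10.3 |
| 0.20 | 54.5% | 44.4% | 10.1 | 50.0% | 37.5% | 12.5 |

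**Step 2. Other shapes of exposure.**
- Fixed cycles. The window is (cycles − 1) × 28 + 5 + 30 days, taking Day 5 as the last dosing day in both arms. Six cycles give 175 days (5.75 months) and four give 119 days (3.91 months). Incidence = 1 − exp(−hW). At h = 0.10 this is 43.7% against 32.4%. At h = 0.03 it is 15.8% against 11.1%. Six against five cycles gives gaps of 2.4 to 5.4 points for h from 0.03 to 0.10.
- Treatment until death at the plan's medians, exponential, plus 30 days: gaps of 4.6, 5.5 and 5.7 points at h = 0.03, 0.05 and 0.10.
- Equal durations: no gap.

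**Step 3. Risk concentrated early.** Let the hazard be h₁ = 0.30 for two months and h₂ afterwards, with mean exposure again 6 against 4 months. With a = h₁ + 1/m:
- incidence = (h₁/a)(1 − e^(−2a)) + e^(−2a) · h₂/(h₂ + 1/m)
- person-time to first event or end of window = (1 − e^(−2a))/a + e^(−2a)/(h₂ + 1/m)

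| h₂ | Crude, m = 6 | Crude, m = 4 | gap (points) | Person-months, m = 6 / m = 4 | Rate ratio |
|---|---|---|---|---|---|
| 0.02 | 43.2% | 38.9% | 4.3 | 3.41 / 2.45 | 0.80 |
| 0 | 39.0% | 36.4% | 2.6 | 3.66 / 2.54 | 0.75 |

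The last column is the overall exposure-adjusted rate in the longer-treated arm divided by that in the shorter-treated arm. It falls to 0.75–0.80 although the hazards are equal: late, low-risk person-time makes the longer-treated arm look safer.

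**Step 4. Near-universal events.** Any Grade 3 or higher AE was 92% in Phase 2 (Protocol Table 4). Setting h/(h + 1/6) = 0.92 gives h = 1.92. At m = 4 the incidence is then 88.5%, a gap of 3.5 points. Individual Grade 3 or higher terms in that table were 20% to 51%, where there is more room to move.

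**Step 5. Does the planned window cover a common early period?** With two five-day cycles on schedule, the last dose is on Day 28 + 5 = 33, and the window runs to Day 63. Seven- and ten-day regimens run to Days 65 and 68. A Day 1–60 window is therefore covered for subjects who complete two scheduled cycles, unless they die or start other therapy first. Subjects who stop after one cycle are covered only to about Days 35 to 40.

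**The case against.** The window has one definition for both arms; only its realised length can differ. The six-cycle minimum for SGI-110 is advisory and yields to toxicity or progression. The local TC labels are not in the documents and may lead to the same, shorter or longer treatment. The main toxicity is myelosuppression, and Protocol 7.3.1 recommends the first two SGI-110 cycles without dose modification regardless of count recovery, so early concentration of risk is plausible and the gap then shrinks. The cycle summaries in SAP 7.4.1 would show an exposure imbalance, all AEs are listed, and 30- and 60-day mortality is already a fixed-window comparison. The named endpoint is incidence and severity, which percentages by grade deliver. No AE test is planned.

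All of this stands as a limit on size and seriousness. It does not close the gap: the exposure table would reveal an imbalance without correcting for it, and the mortality measure counts deaths, not AEs.

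Two stronger readings are tempting. A reader might infer that SGI-110 will be given for longer and so will show about 9 points more toxicity. The documents do not support that: they give no treatment durations, and the 9 points need both a constant hazard and an assumed 6 against 4 months. A reader might also infer that one exposure-adjusted rate ratio would solve the problem. Step 3 shows that it can err in the other direction.

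**Conclusion.** The point holds as a minor gap in the safety analysis. AE summaries are crude percentages over a window that follows time on treatment, the duration rules differ by arm, and nothing planned separates more events per month from more months observed. Whether this will distort the comparison, and in which direction, cannot be known from the documents.

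Under an assumed mean time at risk of 6 against 4 months and equal constant hazards of 0.05 to 0.20 per month, the spurious gap is about 6 to 10 points. It is about 3 to 4 points if risk is concentrated in the first two months or the event is near-universal, and zero if durations are equal. No primary conclusion or error rate is affected, because AEs sit outside the testing hierarchy in SAP 7.3.7.

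**What to change.** Keep the existing n (%) tables. Add to SAP 7.4.2, for Grade 3 or higher AEs, serious AEs and the most frequent Grade 3 or higher terms:

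- **(a) n (%) in a common fixed-day window from C1D1**, for example Days 1 to 60, in line with the 60-day mortality measure. Define it in days rather than as Cycles 1 and 2, because cycles can be prolonged (SAP 7.4.1) or started early (Protocol 7.4).
- **(b) Cumulative incidence of first event by arm over the treatment-emergent window**, read at common time points. State in advance whether death, and the end of the window through treatment discontinuation or alternative therapy, are competing events or censoring. The choice matters. If the end of the window is a competing event, the curve's final level still depends on treatment length. If it is censoring, stopping treatment is assumed to be unrelated to AE risk.

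If rates per patient-year are also shown, give them separately for the early and later periods, since a single rate assumes a constant hazard.

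The cost is a few extra descriptive tables or plots from dosing, death and AE dates already collected. The fixed window says nothing about late toxicity and is only partly observed in subjects who stop during Cycle 1, so (a) and (b) should be read together. Specifying them now avoids a choice made after an imbalance is seen.
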